The non-inferiority limit for the above 4 secondary outcomes is 1 day, 3%, 4%, and 2%, respectively, i.e. the intervention will be deemed non-inferior if the difference between the allocated groups (intervention – control) is less

than 1 day, 3%, 4%, and 2%, respectively. Therefore, the intervention will be deemed non-inferior if the upper limit of the 95% confidence interval lies below 1 day, 3%, 4%, and 2%, respectively.

Sample size for comparison of 2 means (for the first secondary outcome: time to full clinical recovery) and 2 proportions (for the other three secondary outcomes) for a non-inferiority trial was calculated with the following assumptions:

- 1-β = 0.80
- Allocation ratio (intervention/usual care) = 1
- Design effect (DE) = 1 + ρ(n-1)
- n = number individuals per cluster
- ρ = intracluster correlation coefficient
- · We account for the clustering at the level of the individual physician
- n = 50 patients per cluster
- ρ = 0.025 (Previous studies have illustrated that in primary care ICCs for clinical outcomes are lower than those for process outcomes and the ICC for adverse effects to be around 0.025)(28)
- Resulting DE = 2.225
- to account for multiple testing (n=4), we have applied the Bonferroni-Holm correction, generally considered to be a rather conservative approach to control the family-wise error rate.(29) Therefore, our significance levels for the 4 secondary outcomes were 0.0125 (α /4), 0.167 (α /3), 0.025 (α /2), and 0.05 (α /4), respectively.

Secondary outcome		Preliminary sample size	Significance level (α)	Design effect (DE)	Total sample size (preliminary sample size * DE) for this outcome
1.	Time to clinical recovery (days)	575	0.0125	2.225	1280
2.	Additional investigations at index and/or during follow-up (%)	2079	0.0167	2.225	4626
3.	Re-consultations during follow-up (%)	2312	0.025	2.225	5144
4.	Antibiotic prescribing rate during follow up (%)	1906	0.05	2.225	4240

Taking into account the required sample size for these analyses of the primary study outcome and the secondary outcomes, aiming to recruit a **total sample size of 6111 patients** will be sufficient. Considering we previously recruited 8962 and 3981 acutely ill children in Belgium, this seems feasible.

11.1.2 impact of Covid on the primary outcome and revised sample size calculation during the trial

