Imputation techniques are not applicable in this dataset.

Statistical Methodology

Statistical Procedures

-

Baseline characteristics & Clinical features

Presentation of baseline characteristics of the study population and comparability of the two arms will be based on the following variables:

- Age (median and 25-75 percentiles)
- Gender (percentage)

Baseline characteristics and clinical features will be reported using frequencies and percentages, means and standard deviations or medians and interquartile ranges, and minimum / maximum, as appropriate.

Primary endpoint

For the analysis of the primary outcome, we will use a mixed-effects logistic regression analysis to account for the clustering at practice level. The child's age and study arm will be included as predefined covariates in the model. We will do this using R software using the 'glmer' function of the 'lme4' package. Results will be reported by an odds ratio (OR) with 95% confidence intervals.

Multiple imputation will be applied to deal with missing data. Ten complete datasets will be constructed and analysed. The 10 results will be combined into a final result following Rubin's rule.

We will analyse the primary endpoint according to the intention-to-treat (ITT) approach, given the pragmatic nature of our trial.

The participating physicians were asked to recruit children with an acute illness consecutively. GPs were likely to have breached the assumption of consecutive inclusions if they:

- recruited fewer than 10 patients per year;
- performed a POC CRP test on nearly all (>90%) of the included children; and/or
- included nearly exclusively children (>90%) based on a negative result on all three items of the clinical decision tree that do not need antibiotics and exclude those that might need antibiotic treatment.

Apart from the intention-to-treat analysis, a per protocol sensitivity analysis will be performed only considering physicians who have recruited children consecutively.

Secondary endpoint – Proportional measures

We will provide a descriptive analysis of the proportion of subjects with the outcome of interest for each randomization group.

A mixed-effects logistic regression model will be employed to address clustering at the practice level. The child's age and study arm will be included as predefined covariates in the model. Odds ratios, along with their corresponding 95% confidence intervals will be reported.

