Null hypothesis. The diagnostic algorithm including a standardized clinical assessment, a POC CRP test and safety netting advice is inferior to usual care in terms of the number of days until subjects reach full clinical recovery.

Analysis. We will conduct a descriptive analysis to determine the median time to recovery for each randomization group. IQR will also be provided for each group.

For graphical representation, Kaplan-Meier curves will be generated. These curves will be used in combination with a log-rank test to compare the survival curves of the randomization groups.

Additionally, will employ a mixed-effects Cox regression model to address clustering at the practice level. The child's age and study arm will be included as predefined covariates in the model. Hazard ratios, along with their corresponding 95% confidence intervals, will be reported.

Exploratory endpoints – Proportional measures

We will provide a descriptive analysis of the proportion of subjects with the outcome of interest for each randomization group.

A mixed-effects logistic regression model will be employed to address clustering at the practice level. The child's age and study arm will be included as predefined covariates in the model. Odds ratios, along with their corresponding 95% confidence intervals will be reported.

••

Exploratory endpoints – Satisfactory measures

Statistical analysis not applicable due to the qualitative nature of the data.

Upon transcription of the interviews verbatim, an inductive thematic analysis approach is employed to analyse the data. The entire data analysis process was facilitated using qualitative data analysis software QSR NVIVO software version 12 (QSR International Pty Ltd, Melbourne, Australia).

Findings will be centred on main themes and subthemes closely aligned with the research inquiries and reflective of the interview content. In addition, illustrative quotes will be included.

Exploratory endpoints - Cost-effectiveness of the intervention

Different types of economic evaluations will be conducted to compare participants in the intervention group with those in the control group:

- **Costing study** to comprehend the overall cost structure, identify significant cost drivers, and compare the cost impact.

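### The four secondary non-inferiority rules are set on absolute differences, but the SAP plans no practice-clustered confidence interval for any of those differences

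*SAP*

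**What the plan says.** **Protocol.** Section 4.2 gives each of the four secondary outcomes a null hypothesis of inferiority. Section 11.1.1 defines the contrast as intervention minus control and gives the rule: "the intervention will be deemed non-inferior if the upper limit of the 95% confidence interval lies below 1 day, 3%, 4%, and 2%, respectively". Recovery was sized as a difference in means: "Sample size for comparison of 2 means (for the first secondary outcome: time to full clinical recovery"), with the other three sized as differences in proportions. Section 11.3.3 names only a mixed-effects logistic regression for the secondary outcomes and mentions no difference measure.

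**SAP, proportions.** Under the heading for secondary proportional measures, the SAP plans "We will provide a descriptive analysis of the proportion of subjects with the outcome of interest for each randomization group". A mixed-effects logistic model then follows: "Odds ratios, along with their corresponding 95% confidence intervals will be reported".

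**SAP, recovery.** The SAP restates the null that the algorithm "is inferior to usual care in terms of the number of days until subjects reach full clinical recovery". The analysis is then: "We will conduct a descriptive analysis to determine the median time to recovery for each randomization group", with interquartile ranges, Kaplan-Meier curves, a log-rank test and a mixed-effects Cox model: "Hazard ratios, along with their corresponding 95% confidence intervals, will be reported".

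**SAP, Presentation of Results.** Table 1 covers outcomes by arm, with mean and SD, median and IQR, or event counts and percentages. Table 2 has columns for the odds ratio with its 95% CI and the p-value. No margin appears in the available SAP text.

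**The concern.** A non-inferiority verdict needs one estimate on the scale of the margin, with an interval that respects the clustering. The protocol supplies the scale, the margins and the limit to inspect. The SAP supplies clustered intervals only for odds ratios and a hazard ratio. An odds ratio or hazard ratio judged against 1, or a log-rank test, asks whether the arms differ. It does not ask whether an excess as large as the margin has been excluded.

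The gap is wider for recovery. The rule is in days and was sized on means, but the number of days that a hazard ratio represents depends on the shape of the recovery-time distribution, so there is no unique conversion.

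What is at stake is the word safely in the research question. Protocol 4.1 asks that these four outcomes be weighed together with any fall in prescribing, and each was given its own margin and sample size.

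**Working it through.** **Step 1. On which scale was the trial sized?** Inputs from protocol 11.1.1: power 0.80 (z = 0.8416), 1:1 allocation, and alphas 0.0125, 0.0167, 0.025 and 0.05. Sidedness is not stated; I took alpha as one-sided. N is the total before the design effect.

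- Recovery, no true difference: N = 4 × SD² × (z_alpha + z_beta)² / margin² = 4 × 3.89² × (2.2414 + 0.8416)² / 1² = 575.3. Stated: 575.
- Investigations: N = 2 × [0.098 × 0.902 + 0.090 × 0.910] × (2.1272 + 0.8416)² / (0.03 + 0.008)² = 2 × 0.1703 × 8.814 / 0.001444 = about 2079. Stated: 2079.
- Follow-up antibiotics: N = 2 × [0.08 × 0.92 + 0.07 × 0.93] × (1.6449 + 0.8416)² / (0.02 + 0.01)² = 2 × 0.1387 × 6.183 / 0.0009 = 1906. Stated: 1906.
- Re-consultation: N = 2 × [0.34 × 0.66 + 0.33 × 0.67] × (1.9600 + 0.8416)² / (0.04 + 0.01)² = 2 × 0.4455 × 7.849 / 0.0025 = about 2797. Stated: 2312, which I could not reproduce. That is a separate matter.

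Three of the four figures reproduce with difference-scale formulas. The sizing agrees with the rule as written.

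**Step 2. Rule against planned output.**

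| Outcome | Protocol rule | SAP inference | SAP description by arm |
|---|---|---|---|
| Recovery | difference in days, upper limit < 1 | log-rank test, Cox HR | median and IQR; Table 1 format also allows mean and SD |
| Investigations | risk difference, upper limit < 3 points | OR | proportion; events/n |
| Re-consultation | risk difference, upper limit < 4 points | OR | proportion; events/n |
| Follow-up antibiotics | risk difference, upper limit < 2 points | OR | proportion; events/n |

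The quantity in the second column has no planned clustered interval in any row.

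**Step 3. Can the planned output and the rule diverge?** Assumptions: 3500 per arm (7000 / 2, no losses), design effect 2.225 from protocol 11.1.1, and a simple design-effect approximation to the mixed model. Take re-consultation at 36% against 34%.

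- Difference: SE = √{2.225 × [0.34 × 0.66 + 0.36 × 0.64] / 3500} = 0.0170. CI = 0.020 ± 1.96 × 0.0170 = -1.3 to +5.3 points. The upper limit exceeds 4, so the rule fails.
- Odds ratio: (0.36/0.64) / (0.34/0.66) = 1.092. SE(log OR) = √{2.225 × [1/(3500 × 0.34 × 0.66) + 1/(3500 × 0.36 × 0.64)]} = 0.0748. CI = 0.94 to 1.26, non-significant.

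So Table 2 would show no significant difference where the protocol rule is not met.

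**Step 4. What happens at the planning values?** Same assumptions; each upper limit is the difference plus 1.96 SE.

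- Investigations, 9.0% against 9.8%: -0.8 + 1.96 × 1.04 = +1.2 points (margin 3).
- Re-consultation, 33% against 34%: -1.0 + 1.96 × 1.68 = +2.3 points (margin 4).
- Follow-up antibiotics, 7% against 8%: -1.0 + 1.96 × 0.94 = +0.8 points (margin 2).
- Recovery, 4.06 against 4.15 days: -0.09 + 1.96 × 3.89 × √(2 × 2.225 / 3500) = +0.18 days (margin 1). With 1750 per arm, assumed because the SAP expects substantial app drop-out, it is +0.29 days.

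All four pass.

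**The case against.** The strongest reply is that the protocol has already settled what matters: direction, scale, four margins and a 95% upper limit. Nothing in the SAP withdraws them, and both documents fix the clustering level and the model family for the proportions. That stands. A reader might infer that the whole non-inferiority criterion would be chosen after the data are seen. The documents do not support this, because only the estimator and its interval are left open.

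It can also be said that the SAP does offer something on the difference scale. Table 1 gives outcomes by arm, so point differences can be read off. That stands too; what is missing is the clustered interval.

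For the proportions, the odds-ratio limit could be converted at the observed control rate. This nearly recovers the rule. For re-consultation the largest observed excess that passes is 0.60 points after conversion against 0.68 directly. But the SAP does not plan the conversion, and it can tip a close case: follow-up antibiotics at 8% in both arms has a direct upper limit of +1.9 points (passes 2), while the odds-ratio limit of 1.29 converts to +2.1 (fails).

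Three further inferences go too far:

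- That reliance on the hazard ratio would reverse the one-day verdict. A Weibull distribution matching the planning mean of 4.15 and SD of 3.89 has shape about 1.07. A lower HR limit of 0.85 (assumed) then means 4.15 × (0.85^(-1/1.07) - 1) = +0.68 days, still under 1. The lack of a unique conversion stands; a predicted reversal does not.
- That the SAP equates non-significance with non-inferiority. It nowhere says so. The risk lies in how Table 2 may be read.
- That the confidence level belongs to this point. Protocol 11.1.1 says "to account for multiple testing (n=4), we have applied the Bonferroni-Holm correction" for the sizing, yet states its rule with 95% intervals. That conflict lies within the protocol and needs its own treatment.

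Finally, part of the SAP has been removed from the available copy, and the recovery text begins without a heading, so a margin could have stood in lost text. The analysis paragraphs for both outcome types and the layout of Table 2 are visible, however, and none contains a difference with an interval.

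**Conclusion.** The concern holds in a limited form and should be fixed. The protocol decides non-inferiority on the upper 95% limit of an absolute difference. The available SAP text plans no practice-clustered interval for any of the four differences, and its inferential output addresses no difference rather than the margins. For the proportions the gap is one of planned method and can be bridged approximately; for recovery the planned hazard ratio cannot decide a rule in days without a further assumption.

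The consequence is confined to results near a margin. The re-consultation example shows a non-significant odds ratio alongside a failed 4-point rule, whereas at planning values every outcome passes. The sizes rest on 3500 per arm, a design effect of 2.225 and the protocol's planning rates. The primary superiority analysis is unaffected.

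**What to change.** Before the analysis, amend the SAP as follows.

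1. For investigations, re-consultation and follow-up antibiotics, report a risk difference with a practice-clustered 95% CI, for example standardised from the planned mixed logistic model. Compare its upper limit with 3, 4 and 2 points.
2. For recovery, report a practice-clustered difference in mean days with its CI and compare the upper limit with 1 day. If unrecovered children are censored, use the restricted mean to day 30.
3. Restate the four margins, and add columns for the difference (CI) and the margin to Table 2.
4. Keep the odds ratios, hazard ratio, log-rank test and Kaplan-Meier curves as supportive, and align protocol 11.3.3 with the SAP.

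The cost is SAP wording, a matching line in the protocol and two table columns, plus modest extra programming to obtain the clustered difference in each imputed dataset and combine the results. No new data are needed.
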